2.2 Name and Description of the Investigational Agent

The investigation agent (device) in this trial is Embozene™ Color-Advanced Microspheres.

Embozene™ Color-Advanced Microspheres are spherical, tightly calibrated, biocompatible, nonresorbable, hydrogel microspheres coated with an inorganic perfluorinated polymer (Polyzene™-F). The microspheres intended to occlude vasculature for the purpose of blocking blood flow to a target tissue. They are available in prefilled syringes in a range of sizes suitable for embolic therapy. The microspheres are compressible to enable smooth delivery through the indicated delivery catheter and color-coded by size to allow for easy identification. In this trial, we intend to use **250 µm microspheres** (range of microsphere sizes is 250 µm ± 50 µm as per manufacturer, prefilled in yellow syringes).

Embozene™ Color-Advanced Microspheres are supplied in a 20 ml syringe prefilled with 2 ml of product suspended in a non-pyrogenic, sterile transport solution of physiological saline. The total volume of Embozene™ Color-Advanced Microspheres including transport solution is approximately 7 ml. Prefilled syringes of Embozene™ Color-Advanced Microspheres are packaged in a sterile, sealed tray with a peel-away lid. The label indicates the specific size of the microspheres contained in the syringe.

Embozene™ Color-Advanced Microspheres are intended for embolization of arteriovenous malformations and hypervascular tumors, including uterine fibroids and hepatoma, and for embolization of prostatic arteries for symptomatic benign prostatic hyperplasia. This device is not intended for neurovascular use. The device is FDA approved for above indications (FDA approved for treatment of benign prostatic hyperplasia; FDA 510(K) # K180102; 510(k) premarket notification of intent to market the device FDA 510(k) # K141209)

There are no known chemical interactions between Embozene™ Color-Advanced Microspheres and pharmaceuticals.

Additionally, for labeling with Magnetic Resonance (MR) compatibility, the proposed Embozene™ Color-Advanced Microspheres were assessed and met requirements in the Guidance for Industry and Food and Drug Administration Staff Establishing Safety and Compatibility of Passive Implants in the MR Environment. Embozene™ Color-Advanced Microspheres are labeled MR safe in the device Direction for Use (DFU) [attachment 1]

IDE for the purpose of this study was obtained from the FDA (IDE approval # G190316. Approval letter provided [attachment 2].

FDA documents of the device under investigation for approved indications and device DFU are attached to this IRB protocol [attachments 3,4].

FDA reviewed the supplement of IDE application to expand study for significant risk device proposing the addition of 21 patients. FDA has determined sufficient data to support expansion of human clinical trial; this means there are no subject protection concerns that preclude expansion of the investigation. Approved to expand study. Limit 1 US institution and 50 US subjects. [attachment G190316-S003. Letter.EPEX.APPR]

CONFIDENTIAL

This material is the property of the NYU School of Medicine and Langone Medical Center. Do not disclose or use except as authorized in writing by the study sponsor
Interventional Template Version: 12 February 2020

2.2.1 Preclinical Data

Non-clinical tests performed on the Embozene Microspheres, reference device, provide reasonable assurance that the proposed device has been designed and tested to assure conformance to the requirements for its intended use. As the device received FDA approval for additional indications lately (prostate artery embolization), we believe that using the device for geniculate artery embolization (for treatment of knee OA) does not require additional bench, biocompatibility, sterilization, or pre-clinical animal testing beyond what was required for the reference device. All existing testing provided in the previous Embozene Microspheres premarket submissions remains applicable.

Biocompatibility testing provided in the previous Embozene Microspheres premarket notification included: cytotoxicity, sensitization, irritation, sub-acute and sub-chronic systemic toxicity, systemic toxicity- material mediated pyrogenicity, genotoxicity (bacterial mutagenicity, in-vitro chromosome aberration, in-vivo micronucleous assay), implantation, hemocompatibility (hemolysis, partial thromboplastin time, platelet/leukocyte counts). All tests passed, indicating that the device materials are biocompatible for its intended use.

Performance testing provided in the previous Embozene Microspheres premarket notification included: microsphere size distribution, visual inspection, Ph of transport solution, osmolality of transport solution, microsphere suspension, catheter compatibility, and elution test. all tests passed demonstrating the device meets the predetermined performance requirements.

Published literature on preclinical animal studies assessed the biocompatibility, safety, and efficacy of Embozene Microspheres in comparison with the Embosphere predicate and other embolization devices. The devices were evaluated in a porcine kidney model to determine arterial distribution characteristics, inflammation and recanalization, impact on inflammatory tissue and foreign body reaction, and immunohistochemical inflammatory reactions. The results demonstrate a similar biological tissue response between the Embozene Microspheres and the Embosphere predicate device which supports substantial equivalence [18].

A study by Stampfl et al, evaluated the inflammatory response and recanalization after embolization with the embolic agent based on a core and shell design with a hydrogel core of polymethylmethacrylate (PMMA) and a Polyzene-F nanoscale coating in a porcine kidney model [19]. It demonstrated good biocompatibility of the embolic material. As in other spherical embolic agents, recanalization can occur to some degree.

Additionally, for labeling with MR compatibility, the proposed Embozene Microspheres were assessed and met requirements in the Guidance for Industry and Food and Drug Administration Staff Establishing Safety and Compatibility of Passive Implants in the MR Environment.

2.2.2 Clinical Data to Date

Embozene Microspheres have been already investigated in several clinical studies. Stampfl U et al, investigated the safety and efficacy of uterine artery embolization using narrow-size-range polyphosphazene-coated hydrogel microspheres. Results demonstrated that uterine artery embolization with Embozene microspheres is a safe procedure. Its efficacy is demonstrated by high fibroid devascularization and volume reduction rates and significant improvements of clinical symptoms and quality-of-life scores during follow-up [20]. Sneets et al, demonstrated that Polyzene F-coated hydrogel microspheres for uterine artery embolization resulted in good dominant and overall tumor infarction in most patients, with corresponding improvement of symptoms [21].

CONFIDENTIAL

Embolization of the geniculate artery was also investigated for the treatment of recurrent hemorrhage after hip and knee arthroplasty. Kalmar et al demonstrated 100% technical success rate, no procedure-related complications, and effectiveness in patients without underlying coagulopathy in preventing recurrences of spontaneous recurrent hematoma or hemarthrosis of the hip and the knee [22].

Recently, embolization of the geniculate artery was evaluated for the treatment of knee OA. Okuno et al, investigated the effects of embolizing abnormal blood vessels in people with mild to moderate knee OA [6]. Fourteen participants received transcatheter arterial embolization of abnormal branches of the genicular artery using imipenem and cilastatin sodium or 75 μ m Embozene microspheres. WOMAC pain and function scores improved substantially at 1, 4, and 12 months post procedure. No major adverse events occurred. One participant had a moderate subcutaneous hemorrhage at the puncture site that resolved within 1 week.

In a follow-up study, Okuno et al, described the safety and efficacy of transcatheter arterial embolization in 72 patients with mild to moderate radiographic knee OA [23]. Clinical outcomes were evaluated at 1, 4, and 6 months and then every 6 months for a maximum of 4 years. Mean WOMAC pain scores significantly decreased from baseline to 1, 4, 6, 12, and 24 months after treatment (12.1 vs 6.2, 4.4, 3.7, 3.0, and 2.6; all $P < .001$). The WOMS score was evaluated at baseline and at 2 years after embolization in 35 knees and showed significant improvement of synovitis vs baseline ($P < .0016$) and no osteonecrosis or other evidence indicating aggressive progression of degenerative changes. There were no major adverse events related to the procedures. Specifically, there was no incidence of tissue necrosis, dermal ulcers, or peripheral paresthesia in any embolized territory during the follow-up period. Moderate subcutaneous hemorrhage at the puncture site in 12 patients resolved within 1 week. Four of seven patients treated with Embozene showed transient cutaneous color change on the treated knee, which resolved spontaneously within 1 month.

A recent study by Bagla et al, showed improvement in the pain scores in 20 patients with knee osteoarthritis. The mean VAS improved from 76 mm \pm 14 at baseline to 29 mm \pm 27 at 6-month follow-up ($P < .01$). The mean WOMAC score improved from 61 \pm 12 at baseline to 29 \pm 27 at 6-month follow-up ($P < .01$). Self-limiting skin discoloration occurred in 65% patients and 10% of patients developed transient plantar sensory paresthesia.

2.3 Rationale

The rationale is based on a recent article by Okuno Y et al [23]. "The hallmark symptom of knee OA is pain. This is the symptom that drives individuals to seek medical attention and contributes to functional limitation and reduced quality of life [24, 25]. The alleviation of pain is the main motivation for treatment, including nonpharmacologic, pharmacologic, and surgical approaches. Severe and end-stage knee OA is successfully treated with joint replacement surgery, but effective management of mild to moderate radiographic knee OA refractory to conservative treatment can be difficult."

"Although OA was viewed as a "wear-and-tear" disease for many decades, it is now generally accepted to be a low-grade inflammatory disease of synovial joints and a biomechanical whole-organ disease [26]. Angiogenesis is believed to contribute to the genesis of inflammation and particularly to its maintenance [11]. The new increased vascular network provides inflammatory cells access to the synovium and other joint tissues and promotes additional hyperplasia and inflammation in other vessels, leading to bone and cartilage destruction [27]. In addition, studies on OA have shown that angiogenesis may contribute to chronic pain by enabling the growth of new unmyelinated sensory nerves along their path [12, 15]."

The current study seeks to determine whether transcatheter arterial embolization of abnormal neovasculation arising from the genicular arterial branches is safe and effective in the treatment of mild-to-moderate knee OA.

CONFIDENTIAL

2.4 Potential Risks & Benefits

2.4.1 Known Potential Risks

Potential adverse events related to the use of the device from the device from the device insert of directions for use (DFU) [attachment 1] and recent literature [6, 23]:

- Possible adverse events:
 - Incomplete occlusion of vascular beds or territories may give rise to the possibility of post-procedural development of alternative vascular pathways, recanalization, or recurrence of symptoms
 - Post-embolization syndrome including fever, malaise, headache, and myalgia (body aches)
 - Transient, self-resolving cutaneous purpura / skin color change
 - Transient plantar or peripheral sensory paresthesia
 - Synovitis related symptoms including pain, stiffness or limited joint mobility
- Rare adverse events:
 - Allergic reaction and foreign body reactions (e.g., pain, rash, fever, inflammation)
 - Capillary bed saturation and tissue damage
 - Infection
 - Neurological deficits
 - Pulmonary embolization
 - Thrombosis
 - Undesirable reflux, passage/migration or placement of Embozene™ Microspheres, resulting in non-target embolization, ischemia, and / or ischemic infarction.
 - Non-target embolization to lower extremity vasculature resulting in vascular thrombosis and limb threatening ischemia
 - Vessel or lesion rupture
 - Tissue necrosis
 - Dermal ulcer
 - Tendon or ligament rupture
 - Osteonecrosis (rare- not reported in prior studies)
 - Joint infection (rare- not reported in prior studies)

- Very rare adverse events:
 - Cerebrovascular accident (CVA)
 - Death
- Potential adverse events associated with angiography and catheterization of vessels include:
- Nausea, vomiting, and/or allergic reaction anaphylaxis due to iodinated contrast used during embolization procedure (less possible)
 - Contrast-induced renal dysfunction (less possible)
 - Access site-related adverse events: bleeding, infection, hematoma formation, arteriovenous fistula, pseudoaneurysm (rare)

CONFIDENTIAL

- Vessels catheterization associated adverse events: injury to catheterized vessels including vessel perforation, dissection, vasospasm, or thrombosis (rare)
- Infection (rare)

Potential adverse events associated with radiation exposure due to use of knee radiograph and fluoroscopy

- Deterministic radiation risks: Radiation-induced injuries to the skin and underlying tissues, which occur shortly after the exposure (rare)
- Stochastic radiation risks: Radiation-induced malignancy which may occur later in life (rare)

Potential adverse events associated with MRI knee:

- Discomfort (possible)
- Anxiety or claustrophobia (less possible)
- Peripheral nerve stimulation causing tingling or twitching (rare)
- Injury and burns related to metals (very rare, particularly with the MR screening performed prior to entering MR zone and subjects with contraindications to MR will be excluded from the study)
- Pacemaker dysfunction (very rare; subjects with pacemakers will be excluded from the study)
- Skin burns (very rare)
- Tinnitus and hearing loss (very rare)
- Quench (very rare)

Potential adverse events associated with moderate sedation during procedure:

- Over sedation (less possible)
- Nausea, vomiting, and/or allergic reaction to medications / anaphylaxis (rare)
- Respiratory failure, myocardial infarction, and death (rare)

Potential risks associated with study enrollment and ancillary study procedures:

- Discomfort due to blood draws required for the study (possible)
- Minor local discomfort due to the pressure of the ultrasound transducer on the skin during arterial access (possible)
- Inconvenience at having to return for follow-up visits (possible)
- Discomfort, Thrombophlebitis, bruising, bleeding, blood clot, presyncope or syncope (i.e. fainting) due to blood draws required for the study (less possible)
- Psychological discomfort from clinical trial enrollment and completing study questionnaires (less possible)
- Infection from blood draw for lab tests (rare)
- Loss of confidentiality of medical records (rare)

Risk minimization:

The GAE procedure will be performed by fellowship-trained interventional radiologists who have expertise in endovascular techniques, particularly in selective catheterization and transcatheter embolization techniques.

CONFIDENTIAL

Analgesia during the procedures will be provided using conscious sedation if subject opted to receive conscious sedation. The risks of conscious sedation will be minimized by continuous monitoring of heart rate, blood pressure, oxygen saturation, and cardiac rhythm.

The dose area product projected for the procedure is thought to be around 30-75 gray/cm². The effective radiation dose is approximately **0.003 mSv from the x-ray of the knee if needed and a mean of 3.0 to 12 mSv** from angiography of the lower extremity which is about 2-4 years of background radiation and significantly less than that of a cardiac catheterization (reference: Phys Med. 2009 Mar;25(1):25-30). Radiation exposure will be minimized to subjects under the principal of 'as low as reasonably achievable' (ALARA). For example, fluoroscopy will be performed with the lowest acceptable exposure for the shortest time necessary to perform the procedure (genicular artery embolization). Methods to reduce radiation-related adverse events include, but not limited to, tight collimation, use of pulsed fluoroscopy, and judicious image acquisition.

Sterile instruments with a sterile technique will be used to minimize infection risk at the arterial access site. The arterial access site discomfort will be minimized by administration of local anesthesia into the overlying skin and adjacent tissues. Catheter access into the appropriate artery may be performed using ultrasound-guided arterial puncture to prevent inadvertent vessel puncture with subsequent bleeding. Real-time fluoroscopic monitoring of all catheter/wire manipulations will be used to prevent vascular injury.

Cone beam CT, which provides cross sectional anatomic detail prior to embolization, will be available to the operating interventional radiologist. This angiographic technique can mitigate the risk of non-target embolization. The intent of this technique, as well as meticulous angiographic technique will be used to minimize the risk of non-targeted embolization, that could lead to skin or soft tissue/muscle injury.

The subject will be monitored for the risk of an allergic response to iodinated contrast. To minimize the risk of renal dysfunction there will be use of non-ionic contrast agents, and appropriate pre-procedure hydration, when necessary. Subjects who report an allergic reaction to iodinated contrast will be pre-medicated as per routine allergy prophylaxis per standard of care.

2.4.2 Known Potential Benefits

There is no guarantee of benefit to any subject. Potential benefits to the subjects from participating in the study, based on prior clinical data available in the literature [6, 23] are:

- Knee pain reduction
- Physical function improvement
- Synovitis reduction

Other potential benefits under investigation:

- Quality of life improvement
- Delay in progression of disease (i.e. knee OA)

3 Objectives and Purpose

3.1 Primary Objective

The primary objective of the study is to determine the effectiveness of genicular artery embolization in reducing knee pain at 3-months post intervention in patients with knee OA. This will be assessed by evaluating the clinical success rate defined as at least 50% reduction in WOMAC

CONFIDENTIAL

pain score from pre-intervention baseline to follow-up visit at 3 months post-intervention without an increase in baseline incidence of pain medication use or intra-articular injection.

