2.1 Background Information and Relevant Literature

Knee OA is common and major cause of pain and disability. Its prevalence is rising due to an aging population and the high prevalence of obesity [1]. Radiographically confirmed symptomatic knee OA affects approximately 3.8% of people worldwide, and knee and hip OA ranked as the 11th highest contributor to global disability [2]. Disabling symptoms of knee osteoarthritis are seen in an approximately 10 % of people over 55 years old [3]. Therefore, the prevalence and burden of knee OA presents a major challenge for health systems globally [2].

Knee OA is a complex, multifactorial disease with no known cure. Risk factors for knee OA include joint injury, bone and joint shape, muscle strength and mass, obesity, gender, metabolic factors, nutrition and vitamin factors, bone density, psychological health and occupation [4, 5]. Treatment seeks to manage symptoms, but adequate symptom control can be difficult to achieve [4-6]. Evidence-based treatment options for knee OA include intra-articular corticosteroids, exercise, education, weight management, and oral medications such as acetaminophen and non-steroidal anti-inflammatories for minor symptoms [7]. Total knee arthroplasty is generally reserved for those with severe joint disease, pain and functional limitations [8, 9]. On the other hand, moderate knee OA resistant to nonsurgical options, yet not severe enough to warrant joint replacement, does not have an optimal therapy. Therefore, there is still a need to develop an effective, minimally invasive and safe treatment for moderate OA of the knee.

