4.1 Description of Study Design

This study is a single-center, single arm, no sham or placebo, open label, prospective pilot study designed to evaluate the safety and feasibility of geniculate artery embolization for the treatment of knee OA. Enrolled patients will receive angiography and embolization of the one or more geniculate arteries in the affected knee using 250 µm Embosphere microspheres. If both knees are affected, the knee with the higher pain score on electronic VAS will be targeted.

The primary objective is to evaluate the effectiveness of geniculate artery embolization in reducing knee pain at 3 months. The primary objective will be evaluated by the clinical success rate. Clinical success is defined as at least 50% reduction in WOMAC pain score at 3-month follow up visit. 40 patients will be required for this study. The study would accrue 50 patients to account for an attrition rate of 20%.

Change in WOMAC pain score and pain VAS will be used as a measure of efficacy (i.e., pain reduction).

WOMAC questionnaire is a widely used, disease-specific measure for knee OA. It includes 24 questions on daily activities. WOMAC pain score includes five questions regarding pain (pain during walking, stair climbing, nocturnal, rest, weight bearing); each question will be scored using the

CONFIDENTIAL

following points: 0 for no pain, 1 for mild, 2 for moderate, 3 for severe, and 4 for extreme pain. possible score ranges for pain are 0–20. For this purpose, WOMAC Score will be calculated from the Knee injury and Osteoarthritis Outcome Score (KOOS) score which was developed as an extension of the WOMAC score with the purpose of evaluating short-term and long-term symptoms and function in subjects with knee injury and osteoarthritis. This means that the KOOS questionnaires will be administered to patients during visits and the WOMAC score will be calculated from the KOOS scores later at the time of data analysis.

The electronic VAS is a horizontal line with no markings on the scale except “No pain” on the left (score: 0 mm) and “worst possible pain” on the right end of the scale (score: 100 mm). Subjects mark the VAS to indicate their current pain level, with 0 mm representing “No pain” and 100 mm representing “worst possible pain”. In our study, subjects will be asked to mark their pain level on a paper VAS on study questionnaire form and will give a score between 0 to 100, which will be documented on the appropriate eCRF.

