5.1 Inclusion Criteria

In order to be eligible to participate in this study, an individual must meet all the following criteria:

1. 30-80 years of age of any gender and;
2. Kellgren-Lawrence Grade 2, 3, or 4 (in select subjects who have no bony deformity)* knee OA on most recent knee radiograph obtained within 6 months of screening visit and;
3. Knee pain resistant to conservative treatment for at least 3 months* (anti-inflammatory drugs, acetaminophen, physical therapy, muscle strengthening, or intra-articular injection of hyaluronic acid and/or steroids); and
4. Moderate to severe knee pain: pain VAS ≥ 40 mm with 0 representing 'no pain' and 100 'the worst pain imaginable'. If both knees meet inclusion criteria, the one with a higher VAS score will be chosen for the study (i.e., target knee).
5. Willing, able, and mentally competent to provide informed consent and complete study questionnaires in English. The Study questionnaire is validated in English.

A recent study by Padio S et al included subjects with KL grade 4 and published results showed, similar to other studies, clinical reduction in pain score with no added risks. The scientific rationale for adding these subjects with KL grade 4 (severe knee OA with no bone deformity) is based on recent literature data (Citation: JB JS Open Access. 2021 Oct-Dec; 6(4): e21.00085.)

*3 months was chosen because this time interval is thought adequate for knee pain to be considered refractory to conservative care.

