7.1 Study Procedures/Evaluations

7.1.1 Study Specific Procedures

- Medical history
 - Complete medical history will be obtained from medical records if available and/or by interview during clinic visits.
- History of previous and concomitant treatment
 - Knee injections and frequency over the 12 months
 - Medication history over the last month will be obtained during pre and post intervention study visits. Medication history will focus on medications currently taken for the treatment of knee OA; including prescription and over-the-counter medications for pain.
 - Physical therapy and frequency over the 12 months
 - Weight loss / gain
- Focused physical examination:
 - Vital signs (temperature, blood pressure, heart rate, oxygen saturation, height, weight, BMI)
 - Focused knee examination.
 - Lower extremity pulses
- Imaging assessment with knee MRI
 - Baseline and follow-up (at 3 months) knee MRI will be performed.
 - Knee MRI protocol will include: Axial t2 FS, Sagittal PD, Sagittal T2 FS, Coronal PD FS, Coronal PD FS, non-contrast axial and sagittal T1 FS.
 - Imaging variables collected for this study is found in the attached eCRFs
- A discussion of the results of any study specific procedures (e.g., radiographic or other imaging or laboratory evaluations) will be provided to participant after the completion of the study unless these information represent a significant health-related issue.
- Laboratory tests:
 - Baseline and follow-up (at 1-, 3-, and 12-, 18-48 months) laboratory tests will be obtained
- Administration of questionnaires or other instruments for patient-reported outcomes:
 - Electronic VAS
 - KOOS questionnaire
 - Self-reported quality of life EQ-5D-5L questionnaire

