7.4 Concomitant Medications, Treatments, and Procedures

All relevant concomitant medications taken during study participation, as well as treatments and procedures will be recorded on eCRFs. Medications to be reported in the eCRF are concomitant prescription medications, over-the-counter medications and non-prescription medications used pain management. For this protocol, a prescription medication is defined as a medication that can be prescribed only by a properly authorized/licensed clinician.

Note: Subjects will be required to withhold pain medications 24 hours prior to screening and each visit for the evaluation of pain

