10.4.2 Analysis of the Primary Endpoint(s)

The primary endpoint is the clinical success rate defined as at least 50% reduction in WOMAC pain score at 3-month follow-up compared to baseline as a binary assessment.

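### Where the 3-month success rule has a co-treatment clause, it covers only pain medication and injections, so a patient who starts or increases physical therapy or exercise after embolization can still count as a success

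*Combined protocol and SAP*

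**What the plan says.** Clinical success is worded in two ways.

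- **With a co-treatment clause.** The Protocol Summary, Section 3.1 and Section 10.4.1 ask for at least a 50% fall in WOMAC pain from baseline to 3 months "without an increase in baseline incidence of pain medication use or intra-articular injection".
- **Without one.** Section 4.1: "Clinical success is defined as at least 50% reduction in WOMAC pain score at 3-month follow up visit". Section 10.4.2, the primary analysis section: "The primary endpoint is the clinical success rate defined as at least 50% reduction in WOMAC pain score at 3-month follow-up compared to baseline". Section 10.2, which holds the hypothesis and decision rule, also leaves the clause out.

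On the treatments that the clause does not name:

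- Section 2.1: "Evidence-based treatment options for knee OA include intra-articular corticosteroids, exercise, education, weight management, and oral medications".
- Section 5.1, criterion 3, gives the conservative treatments as "anti-inflammatory drugs, acetaminophen, physical therapy, muscle strengthening, or intra-articular injection of hyaluronic acid and/or steroids".
- Section 7.1.1 collects "Physical therapy and frequency over the 12 months", and the Schedule of Activities repeats the previous-treatments item at each visit from 1 month onward.
- Section 7.4 says of concomitant medications, "as well as treatments and procedures will be recorded on eCRFs". It sets no limit on them.
- Sections 3.2 and 4.2.2 make need for physical therapy a secondary outcome at 12 months, with the optional 18-48 month visit added in 4.2.2.

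**The concern.** The plan does not say why the clause is there. The natural reading is that relief obtained from other treatment should not be credited to embolization. On that reading it covers two of the treatments that the protocol regards as active and leaves out others in the same lists. A patient who begins a course of physical therapy in week 2 and reaches the 50% threshold at Month 3 is a success under either wording.

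This matters more here than in a controlled trial. The study is single-arm and open label, so the effect of a co-treatment cannot cancel between groups. The success rate is also tested against 50% and leads to a stated conclusion about further study. Section 10.1 says that no formal SAP will be written, so the protocol is the only place to deal with the matter in advance.

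**Working it through.** **1. The plan's own figures.** Inputs from Sections 10.2 and 10.5: null rate 0.50, alternative 0.75, one-sided, success declared at 16 or more of 23. Exact binomial:

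- P(X ≥ 16 | n = 23, p = 0.50) = 0.0466, stated as 0.047.
- P(X ≥ 16 | n = 23, p = 0.75) = 0.8037, stated as 80.4%.
- Enrolment with 20% attrition: 23/0.8 = 28.75, rounded up to 29; 40/0.8 = 50.

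All of these reproduce.

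**2. A cut-off for 40 patients.** The plan states none. At p = 0.50 and n = 40, P(X ≥ 25) = 0.077 and P(X ≥ 26) = 0.040. The smallest count that keeps the one-sided level at or below 5% is therefore 26. This cut-off is derived here and is not in the plan.

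**3. How new therapy moves the counted rate.** Let p be the success rate without new therapy, s the share of patients who start or increase therapy before Month 3, and f the fraction of starters who would otherwise fail but reach the threshold because of it. Take uptake to be unrelated to whether the patient would have succeeded anyway. Only would-be failures can be converted, so

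counted rate = p + (1 − p) × s × f.

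The documents give neither s nor f. Assumed ranges: s from 10% to 30%, f from 25% to 50%.

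| p | s | f | Counted rate | Misattributed successes among 40 |
|---|---|---|---|---|
| 0.50 | 0.10 | 0.25 | 0.50 + 0.50 × 0.025 = 0.5125 | 40 × 0.0125 = 0.5 (1.25 points) |
| 0.50 | 0.30 | 0.50 | 0.50 + 0.50 × 0.15 = 0.575 | 40 × 0.075 = 3 (7.5 points) |
| 0.75 | 0.10 | 0.25 | 0.75 + 0.25 × 0.025 = 0.75625 | 40 × 0.00625 = 0.25 |
| 0.75 | 0.30 | 0.50 | 0.75 + 0.25 × 0.15 = 0.7875 | 40 × 0.0375 = 1.5 |

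**4. Effect on the decision when the rate without therapy is 50%.**

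| Counted rate | P(≥ 16 of 23) | P(≥ 26 of 40), derived cut-off |
|---|---|---|
| 0.50 | 4.7% | 4.0% |
| 0.5125 | 5.9% | 5.6% |
| 0.575 | 16.9% | 21.3% |

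**5. Whether the data as described would show it.** Section 7.1.1 states a 12-month window for physical therapy. At the 3-month visit that window holds about 12 − 3 = 9 months before the procedure and 3 months after it. Unless the forms date the courses, new therapy cannot be told from old.

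**The case against.** Several points on the other side stand.

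- **Other safeguards exist.** A reader might infer that the clause is the trial's only protection against co-treatment. It is not. Pain must have resisted conservative treatment for at least 3 months (5.1), an injection of the same knee in the previous 3 months excludes (5.2), and pain medication is withheld for 24 hours before visits (7.3, 7.4). A refractory population makes 50% relief from therapy alone less likely. But criterion 3 joins its treatments with an or, so earlier physical therapy is not required and a first course after embolization remains possible.
- **Physical therapy is not confined to one 12-month analysis.** Section 4.2.2 adds the later optional visit, and Section 10.4.3 promises an estimate for each secondary outcome at each time. The text is mixed on this. None of it reaches the 3-month success decision.
- **The forms are not supplied.** They may already date therapy courses, in which case the data-collection part of the fix is met.
- **A larger effect is easy to infer.** Applying 25% to 50% to all 4 to 12 starters gives 1 to 6 misattributed successes. That counts patients who would have succeeded anyway. At a 50% rate, about 6 of 12 starters would otherwise fail, so 6 conversions would need therapy to convert every one.
- **Therapy can follow relief.** Some patients will take it up because their pain eased. Counting them as failures inside the primary definition could bias the rate downward, so the documents do not support extending the primary clause itself.
- **The choice is selective.** Section 2.1 also lists education and weight management, and Section 7.1.1 records weight change. Physical therapy and exercise are singled out here because Section 5.1 places physical therapy and strengthening beside drugs and injections.

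**Conclusion.** The point holds as a gap in the success rule. Where the rule has a co-treatment clause, new or increased physical therapy or exercise before Month 3 falls outside it. Where it has no clause, even added medication and injections are allowed, and the two wordings must be reconciled.

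The documents do not show that the success rate will in fact be inflated, or by how much. Under the assumed uptake and conversion, at a true rate of 50%, about 0.5 to 3 of 40 successes are misattributed. The false-positive chance rises from 4.7% to between 5.9% and 16.9% under the 16-of-23 rule, or from 4.0% to between 5.6% and 21.3% under the derived 26-of-40 cut-off. At a true rate of 75% the misattributed number falls to between 0.25 and 1.5. These figures rest on s and f, which are assumptions, and on uptake being unrelated to would-be response. The case for acting is that the remedy is inexpensive and the plan as written cannot show that the bias is small.

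**What to change.** 1. State in one place whether the co-treatment clause is part of the primary definition, and bring Sections 4.1, 10.2 and 10.4.2 into line with the Protocol Summary, 3.1 and 10.4.1.
2. Leave the list of treatments in the primary definition as it is. Pre-specify in Section 10.4.1 a supporting 3-month success rate, with the same exact 95% CI, that counts as non-success any patient who started or increased physical therapy or supervised exercise for the target knee between Day 0 and the 3-month visit. Report how many primary successes are affected.
3. At Visits 5 and 6, make sure that the treatment history separates therapy since Day 0 from earlier therapy and covers supervised exercise, which Section 7.1.1 does not list.

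The cost is a few sentences of analysis text and, if the forms lack it, one dated question in a history already taken. No extra visit, change in sample size or restriction on care follows. The downside is that patients who take up therapy because their pain eased count as non-success. The supporting rate can only equal or fall below the primary rate, and should be read as a conservative bound.
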